6.8.4 Columbia-Suicide Severity Rating Scale (C-SSRS)

The C-SSRS is a rating tool designed to systematically assess and track suicidal behavior and ideation throughout the study. The C-SSRS is divided into four sections: "Suicide Ideation", "Intensity of Ideation", "Suicidal behavior" and "Actual attempts". "Suicide Ideation" and "Suicidal behavior" consist questions that require a "Yes" or "No" response with options to enter free text. "Intensity of Ideation" questions range from (1) (least severe) to (5) (most severe) with the exception of reasons for ideation question which ranges from (0) (Does not apply) to (5) "Completely to end the pain". For "Actual attempts" category, this is split into actual lethality (ranges from 0 [No damage] to 5, [Death]) and potential lethality (ranges from 0 [Not likely to cause injury] to 2 [behavior likely to result in death despite available medical care]).

7 STATISTICAL METHODS

7.1 General Principles

All data processing, summarization and analyses will be performed using the SAS enterprise 5.1 (SAS 9.3) or higher on SAS hosted environment, unless otherwise specified.

Unless otherwise specified, data will be displayed using the following treatment group labels, in the order presented:

- 1) Double-blind treatment phase
 - Placebo group is labelled as PLCB
 - DSP-5423P 40 mg group is labelled as 40MG
 - DSP-5423P 80 mg group is labelled as 80MG
 - Combined group of DSP-5423P 40 mg and 80 mg group is labelled as Active
 - Combined group of DSP-5423P 40 mg, 80 mg and placebo group is labeled as

Statistical Analysis Plan

Version: 2

Study No. D4904020

Overall

Treatment groups for tables and figures

	PLCB	40MG	80MG	Active	Overall
Efficacy	Y	Y	Y		
Safety	Y	Y	Y	Y	
PK		Y	Y		
Others *	Y	Y	Y	Y	Y

* subject disposition, analysis populations, demographics, psychiatric history, prior and concomitant medications, treatment compliance, treatment exposure. Active group will not be displayed for efficacy analyses.

2) Open-label treatment phase and DSP-5423P treatment period

For tables and figures for the open-label treatment phase and DSP-5423P treatment period, subjects are summarized based on the treatment group in the double-blind treatment phase as, PLCB-to-FLEX DOSE, 40MG-to-FLEX-DOSE, 80MG-to-FLEX DSOE, Active-to-FLEX DOSE, and Overall-to-FLEX DOSE. PK analysis for the open-label treatment phase will be based on the latest dose before the PK sampling.

All data collected will be presented in listings by treatment group, subject, visit and date, unless otherwise specified.

Data will be presented in summary tables by treatment group, assessment and visit (where applicable).

Continuous parameters will be summarized using number of subjects (n), mean, standard deviation (SD), median, minimum (min), and maximum (max) values. Mean and median will be displayed to one more decimal place than the original value; min and max will keep the same number of decimal places. SD will be displayed to two more decimal places from the original value. For the case of CGI-S, another decimal point will be added to mean, median, and SD following the rules above. With regard to Pharmacokinetics parameters, Geometric Mean will be displayed to one more decimal place than the original value, and CV% and Geometric CV% will be done to one decimal place. M1/blonanserin will be displayed to three decimal place.

Categorical parameters will be summarized by presenting the number and percentage of subjects in each category. All percentages will be reported to one decimal place, unless otherwise specified.

In any appropriate analyses, estimates of Least square means (LS Means) and LS Means for the treatment difference will be displayed to one more decimal place than the original value; its SE and 95% CI will be displayed to two more decimal place than the original value or one more decimal place than the original value, respectively. Note that only for the case of analysis of CGI-S, one more decimal will be add on for the parameters above.

Odds Ratio and its 95% CI will be displayed to two decimal places.

Dates will be displayed as YYYY-MM-DD.

All statistical inference will be performed with two-sided tests at the significance level of 0.05 whenever appropriate. All confidence intervals (CIs) will be two-sided with 95% coverage, unless otherwise specified.

All p-values will be rounded to three decimal places; p-values less than 0.001 will be presented as '< 0.001' and p-values greater than 0.999 will be presented as '>0.999' in all tables. Same logic will be applied to adjusted p-value to be obtained in the efficacy primary analysis.

7.2 Subject Disposition and Data Sets Analyzed

Subject disposition will be listed and summarized by treatment group and overall, and will include the number and percentage of subjects for the double-blind treatment phase and the open-label treatment phase, the denominator of the percentage will be the number of randomized subjects and the number of the open-label population, respectively. Summaries of subject disposition will be repeated by country for both treatment phases.

For the double-blind treatment phase, the following information will be reported:

- informed consent obtained,
- not enrolled in the wash-out phase; with breakdown by reason for disposition,
- enrolled in the wash-out phase,
- not randomized; with breakdown by reason for disposition,
- randomized,

Statistical Analysis Plan

Version: 2

Study No. D4904020

- not treated in the double-blind treatment phase; with breakdown by reason for disposition,
- treated in the double-blind treatment phase,
- completed the double-blind treatment phase,
- discontinued from the double-blind treatment phase; with breakdown by reason for disposition.

For the open-label treatment phase, the following information will be reported:

- completed the double-blind treatment phase,
- not treated in the open-label treatment phase; with breakdown by reason for disposition,
- treated in the open-label treatment phase,
- Ongoing; displayed ONLY for interim data analysis,
- completed the open-label treatment phase,
- discontinued from the open-label treatment phase; with breakdown by reason for disposition.

The number and percentage of subjects who included in each analysis population will be summarized for the double-blind treatment phase and the open-label treatment phase, where the denominator of the percentage will be the number of randomized subjects and the number of subject treated at least once in the open-label treatment phase, respectively. These summaries will be repeated by country.

For the double-blind treatment phase, the following analysis populations are of interest:

- mITT population,
- PP population,
- Safety population,
- PK population.

For the open-label treatment phase, the following analysis populations are of interest:

- Open-label population,
- DSP-5423P dosed population,
- PK population.

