## **8.3 Criteria before the open-label treatment phase**

### **8.3.1 Inclusion Criteria before the open-label treatment phase**

Subjects who meet the following criterion will enter the open-label treatment phase.

1. Subjects who have completed the 6-week study treatment and all scheduled assessments at Visit 6 in the double-blind treatment phase, and who are considered eligible by the Investigator with no safety concerns

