2.2 Overall Study Design

This study has two main phases:

1. Double-blind treatment phase: Multicenter, randomized, double-blind, placebo-controlled, parallel-group design
2. Open-label treatment phase: Multicenter, open-label, flexible dose design

The flowchart for this study is given in Figure 1.

Figure 1: Study Flowchart

The study consists of 4 phases: the washout phase, the double-blind treatment phase, the Open-label treatment phase, and the follow-up phase.

In the washout phase, placebo will be applied once daily for 1 week (at least 3 days) in a single-blind manner. After the washout phase, subjects will be randomized to one of three treatments: 40 mg of DSP-5423P, 80 mg of DSP-5423P, and placebo, at 1:1:1 ratio in the Double-blind treatment phase. The study drugs will be applied once daily for 6 weeks. Subjects who completed the double-blind treatment phase can enter the Open-label treatment phase. In the open-label treatment phase, DSP-5423P will be applied as flexible dose (40, 60, or 80 mg) once daily for 28 weeks (outside Japan) or 52 weeks (in Japan).

Subjects who completed the open-label treatment phase or who prematurely discontinued the study drug after entering the double-blind treatment phase will undergo the follow-up assessments in 1 to 2 weeks after the termination of the study drug.

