5.3 Open-label population

The open-label population will consist of all subjects who apply DSP-5423P at least once in the open-label treatment phase.

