5.5 DSP-5423P dosed population

The DSP-5423P dosed population will consist of all subjects who apply DSP-5423P at least once during the study. It does not include placebo group subjects who did not apply any DSP-5423P in the open-label treatment phase.

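### SAP 7.2 divides some rows of the open-label tables by a population that does not contain them, so percentages can exceed 100% and open-label non-entry is printed against entrants, not completers

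*SAP*

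**What the plan says.** SAP 7.2 sets denominators by phase, not by row. For subject disposition, "the denominator of the percentage will be the number of randomized subjects and the number of the open-label population, respectively". For the tables of analysis populations they are "the number of randomized subjects and the number of subject treated at least once in the open-label treatment phase, respectively". SAP 5.3 makes the two open-label denominators the same set: "The open-label population will consist of all subjects who apply DSP-5423P at least once in the open-label treatment phase".

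The rows placed under that denominator are wider than it:

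- The open-label disposition table starts from double-blind completers and then lists those "not treated in the open-label treatment phase; with breakdown by reason for disposition".
- The open-label analysis-population table lists the open-label, DSP-5423P dosed and PK populations.

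SAP 5.5 defines the dosed population over the whole study: "The DSP-5423P dosed population will consist of all subjects who apply DSP-5423P at least once during the study". It adds, for placebo, "It does not include placebo group subjects who did not apply any DSP-5423P in the open-label treatment phase". Protocol 8.3.1 admits to open label only "Subjects who have completed the 6-week study treatment and all scheduled assessments at Visit 6 in the double-blind treatment phase", subject to the investigator's judgement of eligibility.

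The double-blind disposition table has the same structure. Rows for consented subjects, washout enrollees and those not randomized are all percentages of randomized subjects.

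Protocol 15.3.1 asks only for numbers of subjects and sets no denominator, so it does not supply another one.

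**The concern.** A percentage in a disposition or population table should be a share of a group that contains the row. Here some rows contain the denominator and extend beyond it (dosed population, double-blind completers). One row, completers not treated in open label, shares no subject with it.

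Long-term safety and efficacy is a secondary objective, and the open-label phase recruits only from completers. The share of completers who do not go on is the simplest measure of how selected the long-term cohort is, and the rule as written does not print that share. The tables are split by original arm, so the dosed row would also show a difference between the active and placebo columns that comes only from the choice of denominator. They are repeated by country, where counts are smaller.

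**Working it through.** **Inputs**

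- Allocation: "40 mg of DSP-5423P, 80 mg of DSP-5423P, and placebo, at 1:1:1 ratio" (SAP 2.2).
- Planned 167 randomized per group, 501 in total; 133 per group before the allowance for discontinuation (SAP 2.3, Protocol 15.1).
- Double-blind completion rate: not stated, so treated as an assumption and varied.
- Open-label entry rate among completers: not stated, varied.
- All randomized active subjects apply at least one patch: an assumption.

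**The plan's own figure.** 133/(1 − 0.20) = 166.25, rounded up to 167 per group, and 3 × 167 = 501. This matches. The 20% is inferred; the exact implied loss is 34/167 = 20.4%, or 133/167 = 79.6% retained. The documents give no expected size for the open-label or dosed population.

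**Dosed-population row.** Let r be randomized per arm, c the completion rate and e the share of completers who enter open label.

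- Open-label population = 3rce
- Dosed population = 2r + rce (both active arms in full, placebo entrants only)
- Printed overall percentage = (2 + ce)/(3ce)
- Printed percentage in each active arm = 1/(ce)
- Printed percentage in the placebo arm = 100%

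At c = 133/167 and e = 1: dosed = 167 + 167 + 133 = 467, open-label = 3 × 133 = 399, and 467/399 = 117.0%. Each active arm prints 167/133 = 125.6%.

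| Completion c | Entry e | Overall | Each active arm |
|---|---|---|---|
| 70% | 100% | 128.6% | 142.9% |
| 79.6% | 100% | 117.0% | 125.6% |
| 79.6% | 95% | 121.4% | 132.2% |
| 79.6% | 90% | 126.3% | 139.5% |
| 90% | 100% | 107.4% | 111.1% |
| 95% | 100% | 103.5% | 105.3% |

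The ratio does not involve r, so the 582 randomized subjects in SAP Appendix II give the same percentages under the same rates. If 2% of randomized active subjects never apply a patch, 117.0% becomes (0.98 × 334 + 133)/399 = 115.4%. Over randomized subjects, the same 467 is 467/501 = 93.2%.

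**Entry and non-entry rows.** Let x be the share of double-blind completers who do not enter. The SAP rule prints x/(1 − x) for non-entry and 1/(1 − x) for completers.

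| True non-entry x | Printed non-entry | Printed completer row |
|---|---|---|
| 5% | 5.3% | 105.3% |
| 10% | 11.1% | 111.1% |
| 20% | 25.0% | 125.0% |

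**Pre-randomization rows.** Every randomized subject has consented and been through washout. The consented row therefore exceeds 100% of randomized subjects with any screening or washout failure, and the washout-enrolled row with any washout failure. The documents give no failure rates, so no size is attached.

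**The case against.** The strongest reply is that nothing is lost. SAP 7.2 prints counts with the percentages, and completers, non-entrants and entrants are rows of one table. Any reader can form the correct share, and no endpoint, test, adverse-event rate or set membership changes. That stands, and it limits the point to presentation. It does not make the printed percentages right, and the distortion in the non-entry row is small when non-entry is rare.

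Three stronger readings are tempting, and the documents do not support them.

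- A reader might take 117% as a minimum. It depends on treating 133/167 as the completion rate. SAP 2.3 describes the sample size as the number needed for the mITT analysis, and mITT keeps discontinuers with one post-baseline PANSS total. The 79.6% is thus an inference, and better retention gives a lower figure.
- A reader might count the PK row as another demonstrated error. SAP 5.6 does define that population over the whole study. But SAP 7.2 lists it separately under each phase, and SAP 7.4 and 7.9 speak of PK membership for the double-blind phase. If the open-label row means subjects with open-label samples, it cannot exceed 100%. The text is ambiguous.
- A reader might want consented subjects as denominator throughout the pre-randomization rows. Subjects who were never randomized have no arm, so that works only in an overall column.

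**Conclusion.** The point holds as an error in descriptive percentages. As written, the dosed-population row exceeds 100% in the affected active column and in the pooled columns once a single dosed 40 mg or 80 mg subject does not enter open label; that conclusion needs no assumed rate. The double-blind completer row exceeds 100% if any completer does not enter. The non-entry row is then always too high, by 0.3, 1.1 or 5 percentage points at 5%, 10% or 20% non-entry.

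The size of the dosed-row excess is conditional: about 103.5% to 129% overall for completion between 95% and 70%, with full entry and all active subjects dosed, and higher if some completers do not enter. The consented and washout-enrolled rows share the defect, with no size available from the documents. The primary analysis and the safety analyses are unaffected. This is a minor correction, worth making because it is nearly free.

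**What to change.** Replace the per-phase denominators in SAP 7.2 with denominators by row:

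- **Open-label entry and non-entry** (completers, treated, not treated and the reasons): double-blind completers.
- **Ongoing, completed and discontinued within open label:** the open-label population.
- **DSP-5423P dosed population:** randomized subjects, or counts only.
- **PK population in the open-label table:** either restrict it to subjects with open-label PK samples and keep the open-label denominator, or use randomized subjects. State which.
- **Pre-randomization rows:** consented subjects in the overall column only, or counts only.

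The cost is one SAP paragraph and matching footnotes in the table shells. No new data are needed, and no analysis population or inferential analysis changes.

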7.3 Important Protocol Deviations

All-important protocol deviations (IPDs), including those leading to exclusion from the PP population will be listed and summarized by treatment group and overall for the randomized subjects. Tables will be further breakdown by country. IPDs for the double-blind treatment phase will be identified at a blind data review meeting before unblinding. IPDs for the open-label treatment phase will also be identified before the data analysis of open-label treatment phase.

Subjects with any deviation of inclusion or exclusion criteria will be listed respectively.

7.4 Demographics and Other Baseline Characteristics

Demographic and baseline characteristics will be listed and summarized by treatment group and overall for the mITT, PP, safety, open-label, PK only for the double-blind treatment phase, and DSP-5423P dosed populations. Summaries will be repeated by race and country for the mITT, safety, and DSP-5423P dosed population.

Standard descriptive statistics will be presented for the following continuous variables:

- Age (years) [Use SDTM variable, AGE.DM]
- Baseline weight (kg);
- Height (cm);
- Baseline body mass index (kg/m^2) [calculated as $(\text{weight}/\text{height}^2)$ where weight is in kg and height is in m, reported to one decimal place];
- Baseline PANSS total score,
- Baseline CGI-S score,
- Baseline DIEPSS total score

The number and percentage of subjects will be presented for the following categorical variables:

- Sex: Female; Male,
- Age (years): <65; ≥65,
- Race: American Indian or Alaska Native; Asian; Black or African American; Native Hawaiian or Other Pacific Islander; White; Other,
- Ethnicity: Hispanic or Latino; Not Hispanic or Latino,
- Country,
- Hospitalization status on the day of informed consent: Inpatient; Outpatient
For Inpatient, within 3 months (90 days); over 3 months; unknown
- Concomitant diseases: Yes; No,
- Baseline CGI-S score; 1; 2; 3; 4; 5; 6; 7,

No formal tests of statistical significance will be performed on the demographic and baseline.

Other baseline measurements, such as laboratory assessments, vital signs and ECG, will be summarized by treatment group and overall with the post-baseline measurements in separate tables respectively.

7.4.1 Psychiatric History

History of schizophrenia will be listed and summarized by treatment group and overall for the mITT, PP, safety, open-label, PK only for the double-blind treatment phase, and DSP-5423P dosed populations. Summaries will be repeated by country for the mITT, safety, and DSP-5423P dosed population.

Standard descriptive statistics will be presented for the continuous variables:

- Number of episode of schizophrenia,
- Age at the first onset of schizophrenia,
- Duration of illness; years since onset of the first episode [calculated as (informed consent date – date of onset date of the first episode) / 365.25 and reported as year with one decimal place],

- Duration of current episode; months since onset of the current episode [calculated as (informed consent date – date of onset date of the current episode) /30.4375 and reported as month with one decimal place],

The number and percentage of subjects will be presented for the following categorical variables:

- Number of episodes of schizophrenia; 1; 2; 3; 4; 5 or more; Unknown,
- Age at initial onset of schizophrenia;
19 or less; 20 to 29; 30 to 39; 40 to 49; 50 or more
- Duration of illness;
<1; >=1 to <5; >=5 to <10; >=10 to <20; >=20 to <30; >=30;
Unknown
- PANSS composite subscale at baseline:
Positive subscale score > Negative subscale score;
Positive subscale score = Negative subscale score;
Positive subscale score < Negative subscale score
- Baseline PANSS total score: <100, >=100 to <120, >=120

7.4.2 Medical History

Medical condition/event will be coded using the Medical Dictionary for Regulatory Activities (MedDRA) [Version 19.1]. All medical condition/event will be listed, and number and percentage of subjects with any medical condition/event will be summarized for the safety population and DSP-5423P dosed population by system organ class (SOC), preferred term (PT), and treatment group.

7.4.3 Prior and Concomitant Medications

Medications received prior to or concomitantly with treatment will be coded by Covance using the WHO Drug Dictionary [March 1, 2014 version], Anatomical Therapeutic Chemical (ATC) Classification codes.

Prior medications and concomitant medications are defined as follows:

Statistical Analysis Plan

Version: 2

Study No. D4904020

Prior medications are defined as those taken prior to initial dose of study medication, ie, those medications with a start date before the date of initial application of study medication in the double-blind treatment phase.

Concomitant medications are defined as those taken during the double-blind treatment phase and the DSP-5423P treatment period as described below. Note that the concomitant and prior medications definitions are not mutually exclusive, ie, a medication can be classified as both prior and concomitant.

For the double-blind treatment phase, concomitant medications are those with a start date on or after the initial application date of double-blind treatment phase and up to the final application date of double-blind treatment phase, or those with both a start date before the initial application date of double-blind treatment phase and an end date on or after the initial application date of double-blind treatment phase.

For the DSP-5423P treatment period, concomitant medications are those with a start date on or after the first date of DSP-5423P treatment but before the final application date of DSP-5423P treatment, and those with both a start date before the initial application date of DSP-5423P treatment and an end date on or after the initial application date of DSP-5423P treatment.

If a start date of medication is missing after applying imputation rules, the corresponding medication will be classified as concomitant medication. Note that this is only applicable if the initial application date of study medication is not missing.

Prior medications and concomitant medications will be listed and summarized for the double-blind treatment phase on mITT population and the safety population by treatment group, and for the DSP-5423P treatment period on the DSP-5423P dosed population. Tables are repeated by country. The number and percentage of subjects taking medication will be summarized by pharmacological subgroup (ATC-Level 3) and preferred names. Also number and percentage of subjects taking any antipsychotics, antiparkinson drugs, psychotropic drugs, or hypnotic drugs will be summarized as well. These categories will be based on ones captured in CRF. Note that listing for concomitant medications in double-blind treatment phase will include medications taken after the final application date of double-blind treatment phase, as well as concomitant medications. Also listing for concomitant medications in DSP-5423P treatment period will include medications taken after the final application date of DSP-5423P treatment, as well as concomitant medications.

The number and percentage of subjects with concomitant use of antiparkinson drugs in the double-blind treatment phase by treatment group, and in the DSP-5423P treatment period will be summarized. The number and percentage of subjects with concomitant use of antiparkinson drugs in the DSP-5423P treatment period will be additionally summarized by treatment duration: Day -1, Week 1 to 2, Week 3 to 4, Week 5 to 6, Week 7 to 12, Week 13 to 24, Week 25 to 36, Week 37 or later, Overall

* Week 1=Day 1 to 7, Week 2=Day 8 to 14

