### 10.3.1 Antipsychotics

Antipsychotics except for the study drug will be restricted as follows:

- For the subjects not treated with antipsychotics at screening  
Antipsychotics will be prohibited from screening until completion of assessments at the last visit (Visit 109 outside Japan or Visit 112 in Japan) of the open-label treatment phase or the discontinuation visit. If a subject completes the double-blind treatment phase and discontinues before entering the open-label treatment phase, antipsychotics will be prohibited until completion of assessments at Visit 6.
- For the subjects treated with any antipsychotics at screening  
The antipsychotics should be tapered and completely discontinued before the beginning of the washout phase. Antipsychotics will be prohibited from the beginning of the washout phase until completion of assessments at the last visit (Visit 109 outside Japan or Visit 112 in Japan) of the open-label treatment phase or the discontinuation visit. If a subject completes the double-blind treatment phase and discontinues before entering the open-label treatment phase, antipsychotics will be prohibited until completion of assessments at Visit 6.

If urgent treatment is required because of psychiatric symptoms such as acute psychomotor excitability during the open-label treatment phase, at the discretion of the Investigator, only one antipsychotic drug excluding depot neuroleptics and blonanserin can be used concomitantly on an as-needed basis. However, all antipsychotics will be prohibited within 48 hours before the PANSS, CGI-S, and C-SSRS assessments. The total duration of concomitant use of antipsychotics for urgent treatment during the open-label treatment phase should be 5 days or less outside Japan, and 10 days or less in Japan.

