#### **(1) From screening until the end of the double-blind treatment phase**

- For the subjects not treated with antiparkinson drugs at screening  
Antiparkinson drugs will be prohibited from screening until completion of DIEPSS assessments at Visit 6 or the discontinuation visit.
- For the subjects treated with antiparkinson drugs at screening  
Antiparkinson drugs will be tapered and completely discontinued before beginning of the washout phase. Antiparkinson drugs will be prohibited from the beginning of the washout phase until completion of DIEPSS assessments at Visit 6 or the discontinuation visit.

If extrapyramidal symptoms occur or worsen during the washout phase or double-blind treatment phase, only one of the antiparkinson drugs listed in Table 11 may be used and the dose may not exceed the maximum daily dose. If the antiparkinson drug is not effective, the drug may be switched to another antiparkinson drug listed in Table 11. If the drugs listed in Table 11 are not available outside Japan, another similar drug at an equivalent dose will be permitted with prior authorization of the medical monitor (Table 1 Emergency Contact Information for outside Japan, p3). If the extrapyramidal symptoms improve, antiparkinson drugs may be tapered or discontinued.

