6.5.2 Prior/Concomitant Medication

If year of the date is missing, the date will be imputed according to the following rules.

End date:

- 1) If ongoing is checked, no imputation will be performed.
- 2) If ongoing is not checked and end date is totally missing, then end date will be imputed as date of the last visit.
- 3) If only day of end date is missing, end date will be imputed as the earlier one of following dates: the last day of that month and date of the last visit.
- 4) If only month (or both month and day) of end date is missing, end date will be imputed as the earlier one of following dates: the last day (Dec31) in that year and date of the last visit.

Start date:

- 1) If start date is totally missing, no imputation will be performed. If the medication is 'started prior to study' (checked in the CRF), then the medication is set to be a prior medication. Otherwise, the medication is neither prior nor concomitant.
- 2) If only day of start date is missing, start date will be imputed as the first day in that month.
- 3) If only month (or both month and day) of start date is missing, start date will be imputed as the first day (Jan01) in that year.

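### For a medication with a wholly missing start date, SAP 7.4.3 assigns concomitant use without looking at the stop date, and SAP 6.5.2 classifies the same record differently

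*SAP*

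**What the plan says.** SAP 7.4.3 defines concomitant use separately for the double-blind phase and the DSP-5423P treatment period. A medication that started before a period counts as concomitant only if it ended on or after the first application in that period. A fallback follows: "If a start date of medication is missing after applying imputation rules, the corresponding medication will be classified as concomitant medication". Its one proviso is "Note that this is only applicable if the initial application date of study medication is not missing". The same section states that a medication may be both prior and concomitant.

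SAP 6.5.2 sets the imputation rules. A start date lacking only the day becomes the first of the month. One lacking the month, or month and day, becomes 1 January. A wholly missing start date is left missing, and start-date rule 1 then assigns a status: "If the medication is 'started prior to study' (checked in the CRF), then the medication is set to be a prior medication". If the box is not ticked: "Otherwise, the medication is neither prior nor concomitant".

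The protocol requires certain drugs taken at screening to be stopped early. Section 10.3.1 says of antipsychotics: "The antipsychotics should be tapered and completely discontinued before the beginning of the washout phase". Section 10.3.5.1 says: "Antiparkinson drugs will be tapered and completely discontinued before beginning of the washout phase". SAP 7.4.3 then tabulates "The number and percentage of subjects with concomitant use of antiparkinson drugs in the double-blind treatment phase by treatment group", and does so again for the DSP-5423P treatment period.

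**The concern.** If a drug is known to have stopped before a period began, it was not used in that period, whenever it started. The ordinary definition in 7.4.3 respects this and the fallback does not. Two subjects who stopped the same antiparkinson drug on the same pre-washout day would be classified differently if the start year is known for one and unknown for the other.

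Concomitant antiparkinson use is a listed safety endpoint (Protocol 6.3, SAP 3.3). False users added to all arms would raise the percentages and tend to narrow the drug-placebo contrast. Antipsychotics are prohibited in the double-blind phase (Protocol Table 10), yet SAP 7.4.3 tabulates their use, so the table could show prohibited use that did not occur.

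The disagreement with 6.5.2 adds a second problem: two programmers working from the same SAP could produce different tables.

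**Working it through.** The plan gives no figure to reproduce, so the check sets the rules side by side.

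**Cases.** Start date (complete, day missing, month and day missing, wholly missing) by started-before-study box (ticked or not) by stop date (before washout, during the double-blind phase, ongoing) gives 4 × 2 × 3 = 24 combinations. The period examined first is the double-blind phase.

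**Complete or partial start date: 3 × 2 × 3 = 18 combinations.** After imputation every record has a start date, and the ordinary definition applies. With a start before Day 1, a drug stopped before washout is never concomitant. There is no defect here.

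**Wholly missing start date: 1 × 2 × 3 = 6 combinations.**

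| Box | Stop date | SAP 6.5.2 rule 1 | SAP 7.4.3 fallback | Judged by stop date |
|---|---|---|---|---|
| Ticked | Before washout | Prior | Concomitant | Not concomitant |
| Ticked | During double-blind | Prior | Concomitant | Concomitant |
| Ticked | Ongoing | Prior | Concomitant | Concomitant |
| Not ticked | Before washout | Neither | Concomitant | Not concomitant |
| Not ticked | During double-blind | Neither | Concomitant | Concomitant |
| Not ticked | Ongoing | Neither | Concomitant | Concomitant |

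- The 7.4.3 fallback gives the wrong answer in 2 of the 6, both with a stop before washout.
- The sections contradict each other outright in the 3 unticked rows.
- In the 3 ticked rows, prior and concomitant can coexist. The fallback is worded to operate after imputation, so read in order the record becomes both. Nothing in 6.5.2 says prior only, and no section says which rule takes precedence.
- Keeping 6.5.2 alone would not be a cure. For an unticked drug that stopped during the double-blind phase it gives neither status, although the drug was in use.

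**DSP-5423P treatment period.** For the 40 and 80 mg groups the first DSP-5423P application is Day 1, so the table is unchanged. For placebo subjects it is the first open-label application. A drug stopped during the double-blind phase then also precedes the period, and the fallback is wrong in 2 stop-date rows × 2 box states = 4 of the 6.

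**Comparison with adverse events.** SAP 6.5.1 sets a wholly missing start date to the earlier of the event's end date and the first dose, when the end date is known. An event that ended before first dose therefore stays before it. Medications have no such protection.

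**Direction of the effect.** Let u be true use in an arm and a the proportion of subjects falsely added. If a is equal across arms and independent of true use, printed use is u + (1 − u)a, and the difference between two arms is multiplied by (1 − a). Here a is the share taking the drug at screening times the share of those whose record has a wholly missing start date and a stop before the period. Neither share is in the documents, so no value of a can be supported.

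**The case against.** The strongest reply is that 6.5.2 rule 1 already covers the record and neither of its branches yields concomitant. If 6.5.2 is the specific rule, the false count does not arise for a drug stopped before washout. This stands in part: the outcome depends on which section is followed. But the 7.4.3 sentence is just as explicit, comes later in the processing order and allows overlap with prior status. A reader cannot tell that 6.5.2 prevails.

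The reach is also narrow. Start date is a collected CRF item (Protocol 10.3), and a year alone is enough for imputation. The outputs are descriptive counts with no planned test. DIEPSS and extrapyramidal adverse events, which also bear on extrapyramidal safety, do not depend on this flag. All of this stands and limits the weight of the point.

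Three stronger readings are tempting and are not supported:

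- *Every medication with an incomplete start date is affected.* Partial dates are imputed and keep the end-date test.
- *Such records are typical, so the antiparkinson or antipsychotic table would be badly distorted.* A start that lies years back is not the same as an unknown year, and the documents give no rates.
- *Subjects would be wrongly dropped from the per-protocol population.* That criterion (Protocol 15.2.2, SAP 5.2) concerns antipsychotic receipt during washout as well as the double-blind phase, and populations are settled at blinded review. The 7.4.3 flag begins at the first double-blind application, and nothing ties the criterion to it.

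**Conclusion.** The point holds for medications with a wholly missing start date. SAP 7.4.3 ignores a known stop date for them, and SAP 6.5.2 gives the same records a different status. Under a literal reading of 7.4.3, drugs known to have stopped before a period are counted as used in it.

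The consequence is a possible overcount in descriptive concomitant-medication tables for both periods, including the antiparkinson-use endpoint. Its size cannot be computed. The narrowing of the treatment contrast is a direction only and rests on the equal-across-arms and independence assumptions above. The primary MMRM (SAP 7.6.1) is unaffected. The correction is worth making because the rule discards information that settles the question and the remedy is small.

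**What to change.** Replace the 7.4.3 sentence with:

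> If the start date is wholly missing, classify the medication separately for each period by its stop date, after the 6.5.2 end-date rules. If the stop date is before the initial application date of that period, it is not concomitant in that period. If it is ongoing, or the stop date is on or after that date, it is concomitant in that period.

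No branch for a missing stop date is needed, because 6.5.2 already sets a missing, non-ongoing end date to the last visit. An ongoing or late-stopping drug with an unknown start might in fact have begun after the period. Counting it as concomitant is a convention that 7.4.3 already adopts.

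Decide prior status separately, relative to the first double-blind application. A stop date before that application is enough to make the drug prior, whatever the box shows. Do not label a drug prior only because it stopped before the DSP-5423P period: in a placebo subject it may have been concomitant in the double-blind phase. Prior status deserves care because the antipsychotic-use subgroup in SAP 7.6.4 depends on it.

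Amend 6.5.2 start-date rule 1 to refer to this rule, so that one rule governs.

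The cost is two edits to the SAP and a small change to the derivation program. Stop dates (Protocol 10.3) and the ongoing flag (SAP 6.5.2) are already collected.
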